Maximizing Visual Outcomes with Eyhance IOLs

NCT05611073

25 Jan 2022

PROTOCOL TITLE: Maximizing Visual Outcomes with Eyhance IOLs

STUDY TREATMENTS: None

Study Objectives:

The objective of this study is to demonstrate which pre-operative biometric findings or measurements could indicate increased intermediate or near vision in a patient receiving an Eyhance IOL.

The objective will be completed by measuring visual outcomes at distance, intermediate, and near when corrected to plano sphere as well as obtaining or reviewing biometric measurements in a controlled setting. In addition, the patients will also fill out a questionnaire to determine their level of spectacle independence and satisfaction.

Clinical Hypothesis:

Eyhance IOLs provide intermediate vision based on benchmark defocus curves. Some Eyhance patients also appear to have vastly improved intermediate and even near vision compared to other patients who have received an Eyhance IOL. This study aims to determine which biometric properties (such as spherical aberration, q value, pupil size, etc) can be targeted for these outcomes. Patients will be assessed for corrected monocular and binocular distance, intermediate, and near vision at plano. Lastly patient satisfaction score between the two groups will also be determined.

OVERALL STUDY DESIGN

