This is a non-interventional prospective, single center, bilateral, non-randomized, open-label, observational clinical study. All patients will have had bilateral implantation of an Eyhance IOL at the time of cataract surgery. These patients will then be assessed in the 1–6-month post-operative period. Patients will be grouped into two arms: “distance with minimal intermediate” and “distance with enhanced intermediate/near” based on mean photopic binocular BCDVA and DCIVA (at 66 cm) of patients with bilateral Eyhance IOLs corrected to plano sphere. The “distance with minimal intermediate” group is defined by BCDVA of 0.1 logMAR or better but a DCIVA of 0.4 logMAR or worse. The “distance with enhanced intermediate/near” is defined by BCDVA of 0.1 logMAR or better and a DCIVA of 0.3 logMAR or better. In addition to binocular BCDVA and DCIVA, monocular measurements will be obtained as well. The two groups will be compared to assess which patient biometric properties (such as spherical aberration, q value, pupil size, etc) lead to an overall increase in near or intermediate vision as well as overall patient satisfaction. Biometric data will be obtained from the Zeiss IOL Master 700, Atlas 9000, and the iDesign.

Duration:

3 months or longer to meet required enrollment.

Administration:

Patients with previously implanted bilateral Eyhance IOLs will be offered the opportunity to participate in the study.

Visit Schedule:

All subjects will undergo 1 visit. At the study visit and after informed consent, the subjects' demographic information will be collected, and the subject will have the following testing:

- 1) Manifest refraction
- 2) Best corrected distance visual acuity
- 3) Distance corrected intermediate visual acuity
- 4) Distance corrected near visually acuity
- 5) Binocular best corrected distance visual acuity
- 6) Binocular distance corrected intermediate visual acuity
- 7) Binocular distance corrected near visually acuity
- 8) Pupil measurements (photopic and/or mesopic – automated and manual)
- 9) Review or remeasurement of biometry (IOL Master 700 or Atlas 9000 topography)
- 10) iDesign measurement

STUDY POPULATION CHARACTERISTICS:

Condition

Patients with healthy eyes and bilateral implantation of Eyhance IOLs.

Number of Subjects:

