Per Green, for multiple variables in a regression analysis, $N = 50 + 8(m)$ per arm should be sufficient for appropriate power, assuming a beta of 0.2 and an alpha of 0.05 for a power of 80%. Assuming 6 variables (pupil size, q value, spherical aberration, AC depth, axial length, average K power), approximately 110 patients (220 eyes) will be required.

Source: Green, Samuel B. "How Many Subjects Does It Take To Do A Regression Analysis." *Multivariate behavioral research* 26 3 (1991): 499-510 .

Inclusion/Exclusion Criteria (all study criteria apply to each study eye unless otherwise indicated):

Inclusions

- 1) Adults, 40 years of age having already undergone uncomplicated cataract removal by phacoemulsification with a clear corneal incision in both eyes.
- 2) Implantation of bilateral Eyhance IOLs (DIB00/DIU***).

- 3) Able to comprehend and willing to sign informed consent and complete all required testing procedures
- 4) Best Corrected Distance Visual Acuity (BCDVA) projected to be 0.10 logMAR (Minimum Angle of Resolution) or better
- 5) Clear intraocular media
- 6) Minimum of two weeks post YAG capsulotomy to treat PCO

Exclusions

Subjects will not be permitted to enroll in this study if they meet any of the following exclusion criteria:

- 1) Any corneal abnormality, other than regular corneal astigmatism (as determined by pre-operative testing) that in the opinion of the investigator would confound the outcome(s) of the study
- 2) Any complication during cataract surgery (capsular tear, vitrectomy, etc)
- 3) History of or current retinal conditions or predisposition to retinal conditions
- 4) Amblyopia or strabismus in either eye
- 5) History of or current anterior or posterior segment inflammation of any etiology
- 6) Any form of neovascularization on or within the eye
- 7) Glaucoma (uncontrolled or controlled with medication)
- 8) Optic nerve atrophy
- 9) Subjects with diagnosed degenerative eye disorders
- 10) Postoperative CDVA worse than 0.10 logMAR (20/25 snellen).
- 11) Subjects who have an acute or chronic disease or illness that would confound the results of this investigation in the opinion of the investigator (e.g. immunocompromised, connective tissue disease, clinically significant atopic disease, etc)

EVALUATION CRITERIA:

The main objective of this study is to demonstrate which biometric characteristics can lead to enhanced intermediate or near vision in patients with prior bilateral Eyhance implantation.

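### The 80% power statement is unsupported: the groups are formed by an outcome cut-off with no planned split, no effect size is given, and 110 patients cannot meet the plan's own per-arm rule

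*Combined protocol and SAP*

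**What the plan says.** The Overall Study Design section describes a non-randomized, single-visit observational study of patients who already have the lens in both eyes. It states that "Patients will be grouped into two arms" on the basis of post-operative binocular acuity. The minimal group has "BCDVA of 0.1 logMAR or better but a DCIVA of 0.4 logMAR or worse"; the enhanced group has the same distance criterion and a DCIVA of 0.3 logMAR or better. Recruitment is open to any patient with bilateral implants. The document gives no quota for either group and no expected split.

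The Number of Subjects section gives the rule N = 50 + 8(m), applied per arm, which "should be sufficient for appropriate power, assuming a beta of 0.2 and an alpha of 0.05 for a power of 80" per cent. It counts six predictors and concludes that "approximately 110 patients (220 eyes) will be required". It states no effect size, SD, split or allowance for loss.

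The second item under Primary Clinical Endpoints is a comparison of biometry between the two groups by multiple regression. The type of regression and the scale of the outcome are not specified.

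**The concern.** A power figure for a two-group comparison needs a difference to detect and the sizes of the two groups. The plan gives neither. Group sizes are whatever the DCIVA distribution at this site produces, and only the total is fixed. The per-arm wording looks like protection for the smaller group, but the total does not deliver the number the wording calls for.

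The study aims to find measurements that would identify, before surgery, patients likely to gain most from the lens. If one group turns out small and no predictor reaches significance, a reader who trusts the 80% could conclude that biometry does not matter. The data might only show that the comparison was weak.

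**Working it through.** **Inputs from the plan.** m = 6; alpha 0.05 (sidedness not stated, two-sided assumed here); power 80%; total about 110 patients (220 eyes).

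**Step 1: the plan's own figure.** 50 + 8 × 6 = 98 per arm, and 2 × 98 = 196 for two arms. The stated 110 is neither 98 nor 196. An even split of 110 gives 55 per arm, 43 short of 98, and any other split leaves the smaller group shorter still. An allowance of about 10% for loss would come close (98/0.9 = 108.9, so 109 as a total; 196/0.9 = 217.8, so 218 if eyes are counted), but the plan states no such allowance.

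**Step 2: is 80% established at the best split?** For an unadjusted comparison of two means with d in SD units:

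- s = √(1/n₁ + 1/n₂)
- power = Φ(d/s − 1.960)
- detectable d at 80% power = (1.960 + 0.842) × s

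At 55/55, s = 0.1907. Power is 35% for d = 0.30, 75% for d = 0.50, 80% for d = 0.534 and 99% for d = 0.80. These values of d are assumptions, because the plan gives none. So 80% at 55/55 is true for one particular difference that the plan does not name. With 98 per arm the detectable d would be 2.802 × √(2/98) = 0.40; at 55/55, power for d = 0.40 is 55.5%.

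**Step 3: effect of the split.** Grant the plan its 80% at 55/55 (d = 0.534), with all 110 patients classified.

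| Split | s | Power for d = 0.534 | d detectable with 80% power |
|---|---|---|---|
| 55/55 | 0.1907 | 80% | 0.53 |
| 44/66 | 0.1946 | 78% | 0.55 |
| 33/77 | 0.2081 | 73% | 0.58 |
| 22/88 | 0.2384 | 61% | 0.67 |
| 11/99 | 0.3178 | 39% | 0.89 |

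The loss is small to 44/66 and material from 33/77 on.

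**Step 4: patients in neither group.** The cut-offs leave out DCIVA values between 0.3 and 0.4. If 10, 20 or 30% of patients fell there (assumed) and the rest split evenly, 99, 88 or 77 patients would remain. Power for d = 0.534 would be 75.7, 70.7 or 65.0%. If acuity is recorded only in whole 0.1 steps this gap is empty; the plan does not say how it is scored.

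**The case against.** **The rule is stated per arm, so the smaller group is considered.** This is fair. A reader might infer that the rule ignores the smaller group, but the text does not support that: read literally, it asks for 98 in each. The defect is that 110 patients in total cannot meet it.

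**Counted in eyes, the rule could be met.** With 220 eyes, 98 per arm needs 98/2 = 49 patients in the smaller group, so a split of 49/61 or closer would do. But the groups are defined by binocular DCIVA, so both eyes of a patient always carry the same label and are not independent observations. No split is secured on this reading either.

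**A continuous outcome would avoid the problem.** With DCIVA itself as the outcome, the split would not drive power in this way. For the overall F-test with six predictors, N = 110 gives 80% power at R² = 0.116. This stands as a limit on the point. However, the plan states no such model and no R², and it makes the two-group comparison a primary endpoint.

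**The direction of imbalance is unknown.** The Clinical Hypothesis section says that "Eyhance IOLs provide intermediate vision based on benchmark defocus curves", which might suggest that the minimal group will be small. The next sentence credits only some patients with vastly improved intermediate or near vision, which could make the enhanced group the smaller one. The documents settle neither.

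**Coefficient inflation.** A reader might infer that an uneven split distorts logistic estimates. The evidence is weak. In a simulation with six predictors, N = 110 and a true log-odds of 0.6 per SD (600 runs per split), the mean estimate was 0.67 with 50% in the smaller group, 0.66 with 20% and 0.73 with 10%. The bias is much the same at an even split as at 20%, and the plan does not name logistic regression.

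**Conclusion.** The point holds in this form: the plan states 80% power that its design does not secure. Three facts carry it. No effect size is given, no split is planned or controlled, and with patients as the unit 110 falls short of the plan's own 98 per arm at every split.

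It would be tempting to say that 80% holds only near an even split. That concedes too much in one direction and claims too much in the other. Without an effect size, 80% is not established even at 55/55, and a large difference (d = 0.80) would keep 92% power at 22/88, though only 71% at 11/99. The figures in the table are therefore conditional on granting the plan its 80% at the best split.

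They also rest on a two-sided 0.05 test, an unadjusted comparison of means and full classification of all patients. They show the size of the loss from imbalance; they do not predict this study's split or the exact power of its six-variable model.

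**What to change.** Delete the 80% statement and the per-arm justification for 110. In their place, state the difference detectable with 80% power at N = 110 by size of the smaller classified group, labelled as unadjusted, two-sided 0.05 and all patients classified: 0.53 SD at 55/55, 0.58 at 33/77, 0.67 at 22/88 and 0.89 at 11/99. Add that these worsen with every patient who falls in neither group.

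Report the observed sizes of both groups, the number unclassified, and confidence intervals for the biometric differences alongside any null result.

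If group membership is modelled by logistic regression, a Firth penalty is a reasonable option when the smaller group is small. It addresses bias and separation and does not recover power, so it is no substitute for restating the power.

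The cost is a change of wording and a less favourable stated power. No extra patients are needed.

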Primary Clinical Endpoints:

- 1) To compare two groups categorized by “distance with minimal intermediate” and “distance with enhanced intermediate/near” based on mean photopic binocular BCDVA and DCIVA (66 cm) of patients with bilateral Eyhance IOLs targeted corrected at plano sphere.
- 2) To determine if any statistically significant differences in biometric data exists between the two groups including pupil size, spherical aberration, q value, etc. that may allow for pre-operative recognition of those patients who could have enhanced benefits of the Eyhance IOL. This will require multiple regression analysis given the large number of variables.
- 3) Comparison of a patient satisfaction survey between the two groups to assess for subjective differences in everyday life to determine if the enhanced vision plays a statistically significant difference in patients’ perceived quality of vision or quality of life.

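### If the spherical aberration is corneal, it overlaps heavily with q value and curvature, so separate coefficients in the six-variable regression can miss a real corneal-shape effect

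*Combined protocol and SAP*

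**What the plan says.** Under Number of Subjects, the combined protocol and SAP sizes the study by counting predictors: "Assuming 6 variables (pupil size, q value, spherical aberration, AC depth, axial length, average K power". Q value, spherical aberration and average K are three separate entries. The rule given, "N = 50 + 8(m)$ per arm should be sufficient for appropriate power", depends only on how many variables there are and has no term for correlation between them. The stated requirement is "approximately 110 patients (220 eyes) will be required".

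Primary Clinical Endpoints, item 2, sets the target: "To determine if any statistically significant differences in biometric data exists between the two groups including pupil size, spherical aberration, q value, etc". It adds: "This will require multiple regression analysis given the large number of variables". The Clinical Hypothesis puts the question in the same form: "This study aims to determine which biometric properties (such as spherical aberration, q value, pupil size, etc) can be targeted for these outcomes".

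On measurement, Overall Study Design says only: "Biometric data will be obtained from the Zeiss IOL Master 700, Atlas 9000, and the iDesign". The documents do not say which instrument supplies spherical aberration, whether the value is corneal or whole-eye, or at what diameter it is computed. They do not mention correlated predictors, a joint test or variable selection.

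**The concern.** Q value describes the asphericity of the cornea and average K its radius. For a conic surface over a fixed aperture, primary spherical aberration is determined by those two quantities. If the protocol means corneal spherical aberration, three of its six variables carry roughly two pieces of information. They are separated only by departures from a conic and by measurement error.

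In a regression holding all six, the spherical-aberration coefficient asks whether that measure matters among patients with the same q value and the same K. That is narrower than the study's question. A corneal-shape effect that is really present can be split between q value and spherical aberration so that neither reaches significance, or chance can decide which gets the credit. The study could then report that neither property helps to identify patients with enhanced intermediate vision. Overall model fit and prediction are not biased. The harm is to attribution, which is what the study sets out to do.

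**Working it through.** **The plan's own figure.** With m = 6, the stated rule gives 50 + 8 × 6 = 98, per arm. This does not reproduce 110 patients, nor does 2 × 98 = 196. That is a separate matter; N = 110 is used below because it is the stated target.

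**Step 1: the overlap.** For a conic cornea, the primary spherical-aberration coefficient is

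c = [(n − 1)/8 × r⁴/R³ × (q + 1/n²)] / (6√5).

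Assumed inputs, none of them in the documents: n = 1.376; r = 3 mm (6 mm zone); q mean −0.25, SD 0.12; R mean 7.7 mm, SD 0.25; scatter in measured spherical aberration beyond the conic part 0.03 to 0.05 micron.

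- Mean of c: 0.047 × 81/456.5 × 0.278/13.42 mm ≈ 0.17 micron. Simulation gives mean 0.174 and SD 0.077.
- Correlation of q value with measured spherical aberration: 0.90 (scatter 0.03) and about 0.81 (scatter 0.05).

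**Step 2: variance inflation.** VIF = 1/(1 − R²), with R² from regressing spherical aberration on q value and K.

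| q SD | Scatter (micron) | VIF, spherical aberration |
|---|---|---|
| 0.12 | 0.03 | 7.2 |
| 0.12 | 0.05 | 3.3 |
| 0.15 | 0.03 | about 10 |
| 0.08 | 0.08 | 1.4 |

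The VIF for q value is of similar size. For K it is only about 1.0 to 1.3 here, so the competition is mainly between q value and spherical aberration.

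**Step 3: whole-eye value.** Suppose variation unrelated to corneal shape is 1 to 1.5 times the corneal SD (assumed). Then R² ≈ 1/(1 + 1²) = 0.5 to 1/(1 + 1.5²) ≈ 0.3, and VIF = 2.0 to 1.43.

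**Step 4: power of a separate test.** At N = 110, six predictors and two-sided alpha 0.05 (sidedness is not stated), an uncorrelated predictor has 80% power at f² = 0.073. Dividing f² by the VIF and using the noncentral F with 1 and 103 degrees of freedom gives:

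| R² | VIF | Power |
|---|---|---|
| 0 | 1.0 | 80% |
| 0.3 | 1.43 | 65% |
| 0.5 | 2.0 | 51% |
| 0.7 | 3.33 | 34% |
| 0.8 | 5.0 | 24% |
| 0.9 | 10 | 14% |

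This assumes that the coefficient keeps its size once q value is in the model.

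**Step 5: does a joint test recover the effect?** Simulations used N = 110, a continuous outcome correlated 0.3 with the driver, q SD 0.12 and scatter 0.03 to 0.05 micron.

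- Outcome driven by the measured spherical aberration, including its non-conic part: the spherical-aberration coefficient has about 23% to 43% power, the joint 2-degree-of-freedom test of q value and spherical aberration 78% to 81%, and spherical aberration with q value left out 86% to 88%.
- Outcome driven by the conic part, with measurement error of SD 0.05 in q: at least one of the two coefficients is significant in 26% to 38% of runs, the joint test in 75% to 78%.
- Two-group outcome, as the plan defines: joint test about 53% to 59%, against 17% to 51% for at least one coefficient.

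**Cost of the joint test.** At N = 110, 80% power needs f² of about 0.090 on 2 degrees of freedom, against 0.073 for one uncorrelated predictor.

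**The case against.** The strongest objection is that the documents never call the spherical aberration corneal. The iDesign is among the listed instruments, and a whole-eye value would share much less with q value and K. This stands: the point has to be conditional, and the whole-eye reading leaves about 65% to 51% power. The loss shrinks but does not vanish.

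Second, the list of six is a count for a sample-size rule, not a model equation. Joint entry with a separate test per coefficient is therefore an inference. That also stands, although it is the natural reading of six counted variables, a multiple regression and an aim framed variable by variable.

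Third, a reader might infer that the spherical-aberration coefficient would be almost powerless, with about 5% power. A simulation does return that figure if the outcome depends only on the conic part, q value is error-free and all other scatter is noise. Under that construction spherical aberration adds almost nothing once q value and K are known, so 5% is simply the alpha level. It does not measure power lost to collinearity and should not be cited.

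Fourth, a reader might infer that spherical aberration also duplicates pupil size. That would follow only if it were computed at each patient's own pupil, which the documents do not say.

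Finally, replacing the separate tests with a block would blur the question of which property matters. This is a good reason to add the joint test beside the full model and not to substitute it.

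**Conclusion.** The concern holds in conditional form. If spherical aberration is corneal and all six variables enter one model, a real corneal-shape effect can go unrecognised in the separate coefficients for q value and spherical aberration. A term with 80% power when uncorrelated would have about 65% down to 14% (variance inflation 1.4 to 10), or about 65% to 51% with a whole-eye value. The joint test outperformed the separate coefficients in every scenario tried, including a two-group outcome.

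The spreads, scatter and whole-eye variation are all assumed. The Step 4 figures are for linear regression; a logistic model for two groups would show similar inflation only approximately. The documents do not support a claim that the six-variable model is invalid or that either measure is certain to be missed. This is a worthwhile, cheap improvement to the analysis.

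**What to change.** 1. State whether spherical aberration is corneal or whole-eye and which instrument supplies it. Compute it at one fixed analysis diameter for all eyes.
2. Keep the six-variable model. Add a joint 2-degree-of-freedom test of q value and spherical aberration as the test of a corneal-shape effect.
3. Report two further models, each with only one of the pair, together with variance inflation factors.
4. State in advance that neither measure will be called unimportant on the strength of its separate coefficient alone.

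The cost is small: added analysis wording, one extra test and two extra models, with no new type of measurement. A positive joint result supports corneal shape and does not single out one named measure. Item 9 of the Visit Schedule allows either the IOL Master 700 or Atlas 9000 topography, so eyes without topography would lack a corneal value. The number of such eyes should be reported.

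### The only listed predictor set omits age, so a pupil-size association could partly reflect age; prespecify age in the endpoint 2 regression

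*Combined protocol and SAP*

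**What the plan says.** Number of Subjects bases the sample size on "Assuming 6 variables (pupil size, q value, spherical aberration, AC depth, axial length, average K power". All six are ocular measurements. This is the only place where the predictors are listed in full. Clinical Hypothesis, Overall Study Design and Primary Clinical Endpoints each name pupil size, spherical aberration and q value and then leave the list open.

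On analysis, Primary Clinical Endpoints (item 2) says only that multiple regression will be needed. No adjustment set is given, and no section names age as a predictor, covariate, stratifier or matching factor.

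Age should nevertheless be available. Visit Schedule states that "the subjects' demographic information will be collected", and the first inclusion criterion uses age: "Adults, 40 years of age having already undergone uncomplicated cataract removal". No upper limit is stated.

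The study has two kinds of aim. Endpoint 2 seeks to recognise, before surgery, the patients likely to benefit. Clinical Hypothesis goes further and asks "which biometric properties (such as spherical aberration, q value, pupil size, etc) can be targeted for these outcomes", and Overall Study Design uses similarly causal language. The design is non-randomized and observational.

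**The concern.** In an observational comparison, a factor related to both a predictor and the outcome distorts that predictor's coefficient unless it is adjusted for. Age is an obvious candidate for pupil size, the first variable on the list. If age is related to pupil size and also to DCIVA by a route other than the pupil, a model without age assigns part of the age effect to the pupil.

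The study could then name pupil size as a property to target when some or all of the association belongs to age. Age also matters for the recognition aim: it is known for every patient before surgery, so a reader will want to know whether pupil size adds anything to it. If age adjustment is left open, it may be decided after the unadjusted result has been seen.

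**Working it through.** **Inputs from the protocol.** Number of Subjects gives N = 50 + 8m, worded as "per arm should be sufficient for appropriate power"; m = 6; alpha 0.05 (taken here as two-sided, since sidedness is not stated); and "approximately 110 patients (220 eyes) will be required".

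**Inputs assumed.** The documents give no correlation between age and pupil size or between age and DCIVA. Pupil-age is taken as 0.3 to 0.6 in size and age-DCIVA as 0.05 to 0.3. The pupil is given no effect of its own, and the other five predictors are taken as unrelated to age, pupil size and outcome.

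**Step 1: the plan's own figure.** 50 + 8 × 6 = 98, or 2 × 98 = 196 for two arms if the wording is literal. Neither equals 110, and no dropout allowance is stated. That is a separate matter, but it affects the cost in step 5.

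**Step 2: false-positive rate for pupil size, continuous DCIVA, N = 110.** The induced correlation is r = r(pupil, age) × r(age, DCIVA). By the Fisher z approximation with five other predictors, the standard error is 1/√(110 − 3 − 5) = 1/√102 = 0.0990. With shift d = atanh(r)/0.0990, the rate is P(Z > 1.96 − d) + P(Z < −1.96 − d).

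| Pupil-age | Age-DCIVA | r | d | Rate |
|---|---|---|---|---|
| 0.3 | 0.05 | 0.015 | 0.15 | 5.3% |
| 0.6 | 0.10 | 0.06 | 0.61 | 9.3% |
| 0.3 | 0.20 | 0.06 | 0.61 | 9.3% |
| 0.6 | 0.30 | 0.18 | 1.84 | 45% |

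**Step 3: effect of adding age.** A simulation of linear regression at n = 110 (4000 replicates per scenario) used pupil-age correlations of −0.2 to −0.5 and age-DCIVA correlations of 0.2 to 0.4. Without age, the rate was 7% at (−0.2, 0.2), 15% at (−0.3, 0.3) and 54% at (−0.5, 0.4). With age in the model it was 4.3 to 5.4% throughout. The 54% rests on a stronger age-DCIVA link than the range in step 2.

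**Step 4: the planned comparison.** Endpoint 2 compares two groups, and patients with DCIVA strictly between 0.3 and 0.4 logMAR belong to neither. Group sizes are not given. Assumed splits from 40%/40% to 75%/10% leave 0.80 × 110 = 88 to 0.85 × 110 ≈ 94 patients. Two-group logistic regression was simulated under these splits, with five other independent predictors. The rate was about 6.5 to 9% at correlations (0.3, 0.2) and about 22 to 36% at (0.6, 0.3).

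**Step 5: cost of age.** With m = 7 the formula gives 50 + 8 × 7 = 106, within 110 if N is a total. Read per arm, it gives 2 × 106 = 212, but 110 is then already short of the 196 needed for six variables. With an assumed overall f² of 0.15, power at n = 110 moves from 85.7% with six predictors to 83.3% with seven. Collinearity alone widens the pupil interval by 1/√(1 − r²), where r is here the pupil-age correlation: about 5% at 0.3 (1/√0.91 = 1.05) and 25% at 0.6 (1/√0.64 = 1.25). Any outcome variation that age explains offsets part of this.

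**The case against.** The best reply is that confounding is not shown. No section says that pupil size varies with age or that DCIVA does. Confounding also needs a path from age to DCIVA that bypasses the pupil, and eligibility narrows the options. Media must be clear. Retinal conditions, glaucoma, optic atrophy, amblyopia and diagnosed degenerative eye disorders are excluded, as is postoperative corrected distance acuity worse than 0.10 logMAR. All eyes have the same lens family, and intermediate acuity is distance-corrected. If age-DCIVA is only 0.05 to 0.10, the rate is 5.3 to 9.3%, close to nominal. This stands, and it is why the range starts at 5%.

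A second reply is that the six variables are a sample-size assumption, not a locked model, and that the open-ended lists elsewhere could admit age. This also stands. A reader might infer that the plan deliberately excludes age from its final model, but the documents show only that age is not prespecified. Likewise, age is never itemised as a data field; its availability is inferred from "demographic information will be collected" and the age criterion.

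A third reply is that, for recognising patients before surgery, a pupil signal that partly carries age can still be useful. That is correct for prediction. It does not answer the causal wording in Clinical Hypothesis and Overall Study Design.

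Finally, one parameter may cost more than it appears to, because the smaller group limits how many parameters a two-group model can support and its size is unknown. That is fair, but it applies equally to the six variables already listed.

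**Conclusion.** The point holds as possible confounding that the plan does not address, with an inexpensive remedy. Age is missing from the only explicit predictor list, is almost certainly on hand, and bears on the causal part of the aim.

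Under the assumed correlations, the false-positive rate for pupil size lies between about 5% and 45% for continuous DCIVA in 110 patients, and reaches at most about 22 to 36% at the high end for the two-group comparison. These figures rest on correlations that the documents do not supply, on the pupil having no effect of its own, on other predictors unrelated to age, and on assumed group splits.

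Two stronger readings should be resisted. One is that a pupil finding in this study would be an age effect; nothing in the documents establishes that. The other is that 45% is the error rate of the planned analysis; it belongs to a continuous outcome in all 110 patients at the top of the assumed range.

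**What to change.** Prespecify age at surgery as an additional covariate in the endpoint 2 regression, and name age as a data item under Visit Schedule. Report the pupil-size coefficient with and without age. Base any statement that pupil size leads to, or can be targeted for, better intermediate vision on the age-adjusted coefficient. The unadjusted result can still serve the recognition aim if it is labelled as such.

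The cost is one extra parameter, a wider interval for pupil size and a few lines of text; no new measurement is needed. When restating the sample size with m = 7, say whether the formula applies to the total or to each arm: 106 fits within 110 only as a total.

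### The plan's per-arm rule gives 98 patients per arm, yet it asks for about 110 patients with no linking step, so the 80% power claim does not follow as written

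*Combined protocol and SAP*

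**What the plan says.** All references are to the combined protocol and SAP.

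- **Number of Subjects** gives the rule N = 50 + 8m and says that this number "per arm should be sufficient for appropriate power, assuming a beta of 0.2 and an alpha of 0.05 for a power of 80"%. It names six variables, so m = 6, and then states that "approximately 110 patients (220 eyes) will be required". It does not label 110 as a total or as a per-arm figure.
- **Overall Study Design** says "Patients will be grouped into two arms". The arms are formed after testing, "based on mean photopic binocular BCDVA and DCIVA (at 66 cm"), so each patient belongs to one group on binocular acuity. No expected split is given.
- **Primary Clinical Endpoints**, item 2, is "To determine if any statistically significant differences in biometric data exists between the two groups", and adds: "This will require multiple regression analysis given the large number of variables".
- **Duration** is "3 months or longer to meet required enrollment", so the length of the study depends on the sample-size figure.

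**The concern.** The rule and the conclusion stand next to each other and do not agree. A reader who puts six variables into the printed rule gets 98 for each of two arms, not 110 for the study. Nothing printed bridges the gap: there is no dropout allowance (each subject has a single visit), no second formula, no allocation ratio and no argument at eye level.

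This is the plan's only justification of size and its only power statement, and enrolment runs until the required number is reached. Depending on how the paragraph is read, the requirement is 98, 110, 196 or 220 patients. The sponsor cannot tell from the text when enrolment is complete, and a reader of the results cannot tell what the 80% refers to.

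**Working it through.** **Inputs.** From Number of Subjects: rule N = 50 + 8m, stated per arm; m = 6; alpha 0.05 (sidedness not stated); power 80%; stated requirement about 110 patients (220 eyes). From Overall Study Design: two arms, defined per patient. Not given anywhere: effect size, split between arms, allowance for losses.

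**Step 1. Try to reproduce 110.**
- Rule per arm: 50 + 8 × 6 = 98. Two equal arms: 2 × 98 = 196.
- 110 − 98 = 12 and 196 − 110 = 86. The word *approximately* covers neither gap.
- Another number of variables: m = 7 gives 106 and m = 8 gives 114. Exactly 110 needs m = (110 − 50)/8 = 7.5.
- An allowance for losses on a single 98: 98/(1 − 0.10) = 108.9, so 109; 98/(1 − 0.11) = 110.1, so 111. An allowance of about 11% would land near 110, but none is stated.

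The figure is not reproduced from what is printed.

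**Step 2. Set 110 against the rule under each reading.**

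| Reading | Rule requires | 110 supplies | Result |
|---|---|---|---|
| Rule per arm, 110 patients in total | 98 patients in each arm | at most 110/2 = 55 in the smaller arm | short by at least 43; 110/196 = 56% of the equal-arm total |
| One pooled regression, group as outcome | 98 patients in total | 110 | met (110/98 = 112%), but *per arm* is wrong |
| N counts eyes, per arm | 98 eyes in each arm | 220/2 = 110 eyes per equal arm | met numerically only |
| 110 patients per arm | 98 patients in each arm | 110 in each arm | met, but the total is 220 patients (440 eyes), which is not stated |

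**Step 3. Examine the eye count.** Groups are set on binocular acuity, so both eyes of a patient always fall in the same group, and 110 eyes in an arm are 55 patients. With two eyes per patient and a within-patient correlation ρ, 110 eyes are worth about 110/(1 + ρ) independent ones. That stays at or above 98 only if ρ ≤ 110/98 − 1 = 0.12. The plan gives no value for ρ and does not make this argument.

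**Step 4. What 80% could mean.** The plan prints no effect size, so this is illustration only. For the overall F test of six predictors in a linear regression (alpha 0.05, noncentrality f² × N, denominator degrees of freedom N − 7):

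| Assumed f² | N = 55 | N = 98 | N = 110 |
|---|---|---|---|
| 0.10 | 33% | 60% | 66% |
| 0.15 | 49% | 80% | 86% |
| 0.20 | 63% | 92% | 95% |

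An f² of 0.15 corresponds to R² = 0.15/1.15 = 13%. The plan does not name the form of its regression, and group membership is binary, so the linear-model F test is only a guide.

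**The case against.** The strongest defence is that *per arm* is a slip. A regression that separates the two groups must use both groups in one model, and this is the reading that best fits the second primary endpoint. The rule then asks for 98, it is worded as a sufficient number rather than a target, and about 110 clears it with a margin of 12. This stands as the likeliest explanation. It shows which correction is probable, not that the text is right: two words would still be wrong and the margin unexplained.

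A second defence uses every printed number. The plan puts 220 eyes beside the 110 patients, applies its entry criteria to each eye and collects monocular measurements. On equal arms that is 110 eyes each, above 98. The arithmetic is sound, so it cannot be said that every per-arm reading fails numerically. As a justification it does not hold, because the groups are defined per patient and fellow eyes are not independent subjects. It also assumes an even split, which the design does not fix.

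A reader might infer more than this: that the study is underpowered, or that 196 is the correct number. The documents support neither. Power cannot be judged without an effect size, and on the pooled reading 110 is more than the rule asks for. The figure of 196 depends on the per-arm wording being intended, on equal arms and on the patient as the unit.

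**Conclusion.** The point holds as a contradiction within the sample-size paragraph. With six variables the printed rule gives 98 per arm, the stated requirement is about 110 patients, and no step connects them, so the 80% power does not follow as written. The size of the discrepancy depends on the reading: a shortfall of at least 43 patients in the smaller arm if the rule is per arm and 110 is the total, or a surplus of 12 if one pooled regression is meant. These figures need only the printed rule, m = 6 and two arms. The power percentages rest on assumed effect sizes and carry no weight in the conclusion. Every reading requires a change of text, and because this is the only power statement, the correction should be made.

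**What to change.** Rewrite the Number of Subjects paragraph. In every case, make the patient the unit of the sample-size statement, do not count 220 eyes as 220 independent observations, and say whether 110 is a total or per arm. Then, according to what the sponsor intended:

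- **One pooled regression:** delete *per arm*; state that the rule requires 50 + 8 × 6 = 98 analysable patients; give the sponsor's own reason for 110 and the effect size behind the 80%. For reference, 98 patients and six predictors give 80% power at f² of about 0.15, and 110 give about 86%. These are illustrations and should not be entered as if they had been planning assumptions.
- **Rule per arm, 110 patients in total:** state that 110 does not meet the rule, and either withdraw the 80% claim or restate it with an effect size and the expected group sizes.
- **110 per arm:** state the total of 220 patients (440 eyes) and the effect size for the 80% claim.

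It would also help to say whether the number counts enrolled or classified patients, since a distance-corrected intermediate acuity strictly between 0.3 and 0.4 logMAR falls in neither group.

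**Cost.** One paragraph of text, with no added patients, visits or tests. If 110 per arm was meant, the rewording discloses a total twice what most readers would now assume. The downside is that the stated power may become less favourable, above all on the per-arm reading with 110 in total.
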